Appendix 2: Inducers and Inhibitors of CYP3A4

Strong CYP3A4 Inhibitors	Strong CYP3A4 Inducers	Moderate CYP3A4 Inducers
Atazanavir	Apalutamide	Efavirenz
Boceprevir	Carbamazepine	Modafinil
Clarithromycin	Dexamethasone	Etravirine
Cobicistat	Enzalutamide	Nafcillin
Conivaptan	Fosphenytoin	Dabrafenib
Curcumin	Lumacaftor	Bexarotene
Danazol	Midostaurin	Avasimibe
Danoprevir	Mitotane	Echinacea
Darunavir	Pentobarbital	
Delavirdine	Phenobarbital	
Diltiazem	Primidone	
Ditiocarb	Rifampicin	
Econazole	Rifamycin	
Efavirenz	Rifaximin	
Elvitegravir	Rimexolone	
Ergotamine	St. John's Wort	
Idelalisib		
Indinavir		
Ketoconazole		
Loperamide		
Lopinavir		
Methimazole		
Midostaurin		
Naloxone		
Nefazodone		
Nelfinavir		
Nilotinib		
Posaconazole		
Ribociclib		
Ritonavir		
Saquinavir		
Stiripentol		
Telaprevir		
Telithromycin		
Terfenadine		
Tipranavir		
Troleandomycin		
Voriconazole		

Appendix 3: Proposed criteria for measurement of treatment response in adult MDS/MPN

CR (presence of all of the following improvements)

 • Bone marrow: $\leq 5\%$ myeloblasts (including monocytic blast equivalent in case of CMML) with normal maturation of all cell lines and return to normal cellularity^a • Osteomyelofibrosis absent or equal to “mild reticulin fibrosis” (\leq grade 1 fibrosis)^b • Peripheral blood^c 
 ○ WBC $\leq 10 \times 10^9$ cells/L ○ Hgb ≥ 11 g/dL ○ Platelets $\geq 100 \times 10^9$/L; $\leq 450 \times 10^9$/L ○ Neutrophils $\geq 1.0 \times 10^9$/L ○ Blasts 0% ○ Neutrophil precursors reduced to $\leq 2\%$ ○ Monocytes $\leq 1 \times 10^9$/L • Extramedullary disease: Complete resolution of extramedullary disease present before therapy (eg, cutaneous disease, disease-related serous effusions), including palpable hepatosplenomegaly • Provisional category of CR with resolution of symptoms:[‡] CR as described above, and complete resolution of disease-related symptoms as noted by the MPN-SAF TSS • Persistent low-level dysplasia is permitted given subjectivity of assignment of dysplasia[*]
Complete cytogenetic remission

 • Resolution of previously present chromosomal abnormality (known to be associated with myelodysplastic, syndrome myeloproliferative neoplasms, or MDS/MPN), as seen on classic karyotyping with minimal of 20 metaphases or FISH^d
Partial remission

 • Normalization of peripheral counts and hepatosplenomegaly with bone marrow blasts (and blast equivalents) reduced by 50%, but remaining $>5\%$ of cellularity except in cases of MDS/MPN with $\leq 5\%$ bone marrow blasts at baseline
Marrow response

 • Optimal marrow response: Presence of all marrow criteria necessary for CR without normalization of peripheral blood indices as presented above. • Partial marrow response: Bone marrow blasts (and blast equivalents) reduced by 50%, but remaining $>5\%$ of cellularity, or reduction in grading of reticulin fibrosis from baseline on at least 2 bone marrow evaluations spaced at least 2 mo apart
Clinical benefit

 • Requires 1 of the following in the absence of progression or CR/partial response and independent of marrow response (cord blood response must be verified at ≥ 8 wk) to be considered a clinical benefit • Erythroid response: 
 ○ Hgb increase by ≥ 2.0 g/dL ○ TI for ≥ 8 wk for patients requiring at least 4 packed red blood cell transfusions in the previous 8 wk ○ Only red blood cell transfusions given based on physician’s judgment for a pretreatment Hgb of ≤ 8.5 g/dL will count in the red blood cell TI response evaluation^{ll} • Platelet response: 
 ○ Transfusion independence when previously requiring platelet transfusions of at least a rate of 4 platelet transfusions in the previous 8 wk ○ Pretreatment $\leq 20 \times 10^9$/L: increase from $<20 \times 10^9$/L to $>20 \times 10^9$/L and by at least 100% ○ Pretreatment $>20 \times 10^9$/L but $\leq 100 \times 10^9$/L: absolute increase of $\geq 30 \times 10^9$/L^e • Neutrophil response: 
 ○ Pretreatment $\leq 0.5 \times 10^9$/L at least 100% increase and an absolute increase $\geq 0.5 \times 10^9$/L ○ Pretreatment, $>0.5 \times 10^9$/L and $\leq 1.0 \times 10^9$/L At least 50% increase and an absolute increase $\geq 0.5 \times 10^9$/L[†] • Spleen response:

 ○ Either a minimum 50% reduction in palpable splenomegaly of a spleen that is at least 10 cm at baseline or a spleen that is palpable at more than 5 cm at baseline becomes not palpable • Symptom response: 
 ○ Improvement in symptoms as noted by decrease of $\geq 50\%$ as per the MPN-SAF TSS scoring < 20 were not considered eligible for measuring clinical benefit.
Disease Progression
(Combination of 2 major criteria, 1 major and 2 minor criteria, or 3 minor criteria from the lists below)
Major criteria

 • Increase in blast count^f 
 ○ $< 5\%$ blasts: $\geq 50\%$ increase and to $> 5\%$ blasts ○ 5-10% blasts: $\geq 50\%$ increase and to $> 10\%$ blasts ○ 10-20% blasts: $\geq 50\%$ increase and to $> 20\%$ blasts ○ 20-30% blasts: $\geq 50\%$ increase and to $> 30\%$ blasts • Evidence of cytogenetic evolution^g 
 ○ Appearance of a previously present or new cytogenetic abnormality in complete cytogenetic remission via FISH or classic karyotyping ○ Increase in cytogenetic burden of disease by $\geq 50\%$ in partial cytogenetic remission via FISH or classic karyotyping • New extramedullary disease 
 ○ Worsening splenomegaly 
 ▪ Progressive splenomegaly that is defined by IWG-MRT: the appearance of a previously absent splenomegaly that is palpable at > 5 cm below the left costal margin or a minimum 100% increase in palpable distance for baseline splenomegaly of 5-10 cm or a minimum 50% increase in palpable distance for baseline splenomegaly of > 10 cm ○ Extramedullary disease outside of the spleen 
 ▪ To include new/worsening hepatomegaly, granulocytic sarcoma, skin lesions, etc.
Minor criteria

 • Transfusion dependence^h • Significant loss of maximal response on cytopenias $\geq 50\%$ decrement from maximum remission/response in granulocytes or platelets • Reduction in Hgb by ≥ 1.5g/dL from best response or from baseline as noted on complete blood count • Increasing symptoms as noted by increase in $\geq 50\%$ as per the MPN-SAF TSS^l • Evidence of clonal evolution (molecular)ⁱ

^a Presence of dysplastic changes, which may be interpreted within the scope of normal range of dysplastic changes, may still exist in the presence of CR as allowed in MDS IWG. Marrow should exhibit age-adjusted normocellularity in CR.

^b If there is no significant fibrosis present on the initial bone marrow biopsy, a second biopsy is not required to prove resolution of fibrosis. Grading of fibrosis in measurement of treatment response should be according to the European Consensus System.

^c Given the current lack of a validated tool to assess complete resolution of symptoms in MDS/MPN, "CR with resolution of symptoms" (a complete resolution of disease-related symptoms as noted by the MPN-SAF TSS in presence of CR) will be a provisional category of disease response.

^d Loss of cytogenetic burden of disease by (via FISH or classic karyotyping) known to adversely affect prognosis is required to reach complete cytogenetic remission. Decrease in the cytogenetic burden of disease must be by $\geq 50\%$ (via FISH or classic karyotyping) to be indicative of a partial cytogenetic response. Given variability of fluorescent

probes used in FISH, cytogenetic normalization via FISH will depend on the performance characteristics of the specific probes used.

^e Resolution of abnormal peripheral blood counts must persist for at least 2 separate analyses over at least 8 wk. In the case of proliferative MDS/MPN, CR will include resolution of thrombocytosis to a normal platelet count ($150\text{--}450 \times 10^9/\text{L}$) and resolution of leukocytosis to $\text{WBC} \leq 10 \times 10^9 \text{ cells/L}$ but $\geq 1.5 \times 10^9/\text{L}$. Hgb should be maintained $>11 \text{ g/dL}$ and platelets $\geq 100 \times 10^9/\text{L}$ without the support of transfusions. Clinical benefit may occur when these changes occur in absence of other changes required for CR or marrow response. Platelet and packed red blood cell TI would be considered for clinical benefit, and duration of TI should be monitored. Reduction in myeloid precursors (promyelocytes, myelocytes, metamyelocytes, nucleated red blood cells) to less than appreciable levels ($\leq 2\text{--}3\%$) and/or $1 \times 10^9/\text{L}$ monocytosis in the absence of infection, cytokine treatment, or other reactive causes.

^f Blasts as measured from the bone marrow.

^g Increase in cytogenetic burden of disease by $\geq 50\%$ (via FISH or classic karyotyping). Given variability of fluorescent probes used in FISH, cytogenetic normalization via FISH will depend on specific probes used.

^h Transfusion dependency is defined by a history of at least 2 U of red blood cell transfusions in the past month for a hemoglobin level $<8.5 \text{ g/dL}$ that was not associated with clinically overt bleeding. Cytopenias resulting from therapy should not be considered in assessment of progression.

ⁱ The identification of new abnormalities using single nucleotide polymorphism arrays or sequencing or a clearly significant increase in mutational burden of a previously detected abnormality. Precise criteria for defining new abnormalities and what exactly constitutes a significant increase in mutational burden are open to interpretation; we suggest that this criterion should be used conservatively based on current evidence.

Appendix 4: Myeloproliferative Neoplasms Symptom Assessment Form- Total Symptom Score (MPN-SAF TSS) Form

Patient initials: _____ **Patient Study ID:** _____

Study Time Point (cycle/day): _____ **Date:** _____

Symptom	1 to 10 (0 if absent) ranking 1 is most favorable and 10 least favorable
Please rate your fatigue (weariness, tiredness) by circling the one number that best describes your WORST level of fatigue during past 24 hours	(No Fatigue) 0 1 2 3 4 5 6 7 8 9 10 (Worst Imaginable)

Circle the one number that describes how, during the PAST WEEK how much difficulty you have had with each of the following symptoms	
Filling up quickly when you eat (Early satiety)	(Absent) 0 1 2 3 4 5 6 7 8 9 10 (Worst Imaginable)
Abdominal discomfort	(Absent) 0 1 2 3 4 5 6 7 8 9 10 (Worst Imaginable)
Inactivity	(Absent) 0 1 2 3 4 5 6 7 8 9 10 (Worst Imaginable)
Problems with concentration (compared to prior to my MPD)	(Absent) 0 1 2 3 4 5 6 7 8 9 10 (Worst Imaginable)
Numbness/ Tingling (in my hands and feet)	(Absent) 0 1 2 3 4 5 6 7 8 9 10 (Worst Imaginable)
Night sweats	(Absent) 0 1 2 3 4 5 6 7 8 9 10 (Worst Imaginable)
Itching (pruritus)	(Absent) 0 1 2 3 4 5 6 7 8 9 10 (Worst Imaginable)
Bone pain (diffuse, not joint pain or arthritis)	(Absent) 0 1 2 3 4 5 6 7 8 9 10 (Worst Imaginable)
Fever (>100 F)	(Absent) 0 1 2 3 4 5 6 7 8 9 10 (Daily)
Unintentional weight loss (last 6 months)	(Absent) 0 1 2 3 4 5 6 7 8 9 10 (Worst Imaginable)

What is your Overall Quality of Life?	(As good as it can be) 0 1 2 3 4 5 6 7 8 9 10 (As bad as it can be)
---------------------------------------	---

Patient signature: _____

Date: _____

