1.2 Secondary Objective(s)

1.2.1 To assess the safety of cobimetinib treatment in CMML.

Secondary Endpoint: Frequency of adverse events (AEs) characterized by seriousness, severity (as defined by CTCAE, version 5.0), duration, and relationship to study therapy.

1.2.2 To assess the complete response (CR) + partial response (PR) rate (as defined by the 2015 MDS/MPN-IWG criteria) with cobimetinib treatment in CMML.

Secondary Endpoint: Proportion of patients achieving CR+PR at any time point.

1.2.3 To assess the long term efficacy of cobimetinib treatment in CMML.

Secondary Endpoints:

- Progression-free survival (PFS) from the time of treatment initiation to 36 months after the start of therapy, the time of progression, initiation of alternative treatment, or death.
- Overall survival (OS) as defined as the time from the initiation of study therapy until death from any cause.

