2 BACKGROUND

2.1 Chronic Myelomonocytic Leukemia

Chronic myelomonocytic leukemia (CMML), with an estimated incidence of 4 cases per 100,000 persons per year, accounts for the vast majority of hematologic malignancies classified as myelodysplastic/myeloproliferative (MDS/MPN) neoplasms.^{1,2} As a disease group, MDS/MPN is characterized by features consistent with ineffective hematopoiesis, such as cytopenias, but also exhibit signs characteristic of myeloid hyperplasia, such as splenomegaly, leukocytosis and debilitating constitutional symptoms. CMML is poor-risk

Table 1: WHO 2022 diagnostic criteria for CMML.

Prerequisite criteria
1. Persistent absolute ($\geq 0.5 \times 10^9/L$) and relative ($\geq 10\%$) peripheral blood monocyto-sis.
2. Blasts constitute $< 20\%$ of the cells in the peripheral blood and bone marrow.
3. Not meeting diagnostic criteria of chronic myeloid leukaemia or other myeloproliferative neoplasms.
4. Not meeting diagnostic criteria of myeloid/lymphoid neoplasms with tyrosine kinase fusions.
Supporting criteria
1. Dysplasia involving ≥ 1 myeloid lineages.
2. Acquired clonal cytogenetic or molecular abnormality.
3. Abnormal partitioning of peripheral blood monocyte subsets.
Requirements for diagnosis
- Pre-requisite criteria must be present in all cases.
- If monocyto-sis is $\geq 1 \times 10^9/L$: one or more supporting criteria must be met.
- If monocyto-sis is ≥ 0.5 and $< 1 \times 10^9/L$: supporting criteria 1 and 2 must be met.
Subtyping criteria
- Myelodysplastic CMML (MD-CMML): $WBC < 13 \times 10^9/L$
- Myeloproliferative CMML (MP-CMML): $WBC \geq 13 \times 10^9/L$
Subgrouping criteria (based on percentage of blasts and promonocytes)
CMML-1: $< 5\%$ in peripheral blood and $< 10\%$ in bone marrow
CMML-2: $5\text{--}19\%$ in peripheral blood and $10\text{--}19\%$ in bone marrow

leukemia of older adults, with an average age of diagnosis of 72 years.³ Even with currently available therapies, the median overall survival is dismal, ranging from 12-29 months.¹ The inferior survival outcomes in CMML are primarily driven by a high risk of progression to acute myeloid leukemia (AML). Allogeneic stem cell transplant for CMML is potentially curative, but relapse rates and transplant-related mortality are high, and few patients are eligible due to advanced age and co-morbidities.

Diagnostic criteria for CMML according

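### Appendix 3 does not make transformation to AML progression by itself, so PFS can miss a documented transformation or date it late

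*Combined protocol and SAP*

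**What the plan says.** Section 1.2.3 runs PFS from the start of treatment to 36 months, "the time of progression, initiation of alternative treatment, or death"; Section 11.6.2 repeats this. Neither names transformation to AML, and there is no leukaemia-free survival endpoint.

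Appendix 3 defines progression as a "Combination of 2 major criteria, 1 major and 2 minor criteria, or 3 minor criteria from the lists below". Within the blast criterion, which is one major criterion, the relevant bands read "10-20% blasts: $\geq 50\%$ increase and to $> 20\%$ blasts" and then "20-30% blasts: $\geq 50\%$ increase and to $> 30\%$ blasts". Footnote f limits the compartment: "Blasts as measured from the bone marrow".

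Table 1 in Section 2.1 gives the prerequisite for CMML: "Blasts constitute $< 20\%$ of the cells in the peripheral blood and bone marrow". The same section says that the poor survival in CMML is "primarily driven by a high risk of progression to acute myeloid leukemia (AML").

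Clinical benefit, one of the components of the primary ORR (Sections 1.1 and 11.6.1), is credited "in the absence of progression or CR/partial response and independent of marrow response".

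**The concern.** The background treats AML as the form of progression that matters most, and the endpoint definition gives it no standing of its own. A patient can leave the disease definition in Table 1 without having progressed under Appendix 3.

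The main consequence is for PFS, the secondary endpoint meant to describe long-term efficacy. A known transformation may be dated later than it occurred, attributed to a different cause or not recorded as an event. The direction is towards a more favourable PFS curve. There is also a narrow consequence for ORR, because clinical benefit is barred by progression as Appendix 3 defines it and not by the state of the marrow.

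**Working it through.** **1. Which rule governs.** Section 10.8 requires the 2015 MDS/MPN-IWG criteria, Section 11.2 points to Appendix 3, and Section 6.4.1 uses the same criteria for discontinuation. Sections 1.2.3 and 11.6.2 do not cite Appendix 3, so the link to PFS is an inference. It is nevertheless the only definition of progression in the document.

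**2. The combination rule.** With M major and m minor criteria, progression requires M ≥ 2, or M ≥ 1 with m ≥ 2, or m ≥ 3.

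| M | m | Progression? |
|---|---|---|
| 1 | 0 | No |
| 1 | 1 | No |
| 1 | 2 | Yes |
| 2 | 0 | Yes |
| 0 | 3 | Yes |

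A blast rise alone is therefore never progression, whatever its size.

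**3. The blast criterion.** For a baseline b in the 10-20% band and a follow-up value f, the criterion needs (f − b)/b ≥ 0.5 and f > 20%. The first condition is f ≥ 1.5b, which exceeds 20% once b is above 20/1.5 = 13.3%.

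| Baseline | Follow-up | Relative rise | 1.5 × baseline | Result |
|---|---|---|---|---|
| 12% | 25% | 13/12 = 108.3% | 18.0% | One major criterion; not progression alone |
| 15% | 22% | 7/15 = 46.7% | 22.5% | No criterion |
| 17% | 25% | 8/17 = 47.1% | 25.5% | No criterion |
| 18% | 26% | 8/18 = 44.4% | 27.0% | No criterion |
| 19% | 28% | 9/19 = 47.4% | 28.5% | No criterion |

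For baselines of 14% to 19%, the criterion is first reached at 1.5 × 14 = 21.0% up to 1.5 × 19 = 28.5%. Values from 20% up to that threshold meet nothing. At lower baselines the criterion is met easily (4% to 25%, for example), but it is still only one major criterion.

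**4. Blood.** Table 1 sets its ceiling in blood and marrow, whereas footnote f counts marrow only. Blood blasts of 20% or more are not a criterion.

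**5. Other routes to progression.** These exist, with limits. Cytogenetic evolution is listed for patients in complete or partial cytogenetic remission, although footnote g is worded more broadly. Footnote h sets aside cytopenias caused by therapy. Footnote i asks for restraint in using molecular evolution.

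**6. What PFS then records.** If no combination is met, the next date available is alternative treatment or death. The text does not say whether alternative treatment is an event or a censoring time. As an event it comes late; as censoring it removes the transformation from the curve.

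**7. Follow-up.** Under Amendment 6, patients still on treatment go to EOT and follow-up (Section 4.1). Those who obtain cobimetinib at the protocol dose and frequency stay in the PFS analysis (Section 11.6.2). For follow-up, Table 5 marks survival contact, every three months, but no marrow, CBC or symptom score. A progression needing several criteria is hard to assemble from such contacts. An AML diagnosis could be learned at one, but on its own it would not be an event.

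**8. The plan's own figures.** The plan gives none for PFS. Its design figures concern ORR. With stopping at r1 or fewer responses in n1 and rejection at r or more in n, the rejection probability is the sum over x = r1 + 1 to n1 of P(X = x; n1, p) × P(Bin(n − n1, p) ≥ r − x). This gives 0.1678 and 0.8028 (newly diagnosed) and 0.1559 and 0.8100 (HMA refractory), as stated. This point does not change them.

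**The case against.** Appendix 3 reproduces a published instrument that the trial adopted openly. The combination rule, the marrow-only footnote and the band above 20% belong to it, so passing 20% was graded and not overlooked. That is fair: this is a design choice with a gap, not a transcription error. Many transforming patients may meet a second major or two minor criteria, and PFS ends at other treatment or death in any case. PFS is descriptive, with no test attached. Unscheduled marrows are allowed when clinically indicated (Table 5, footnote 18). All of this stands, and it limits the problem to a missed or late event.

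A reader might infer that transformed patients will inflate the primary ORR. The documents do not support that as an expected effect. The patient would need a qualifying benefit despite transformation, verification at 8 weeks or more, a symptom score of at least 20 if symptoms are the route, no second major criterion and, with the blast criterion met, at most one minor criterion. One patient is worth 1/14 = 7.1 or 1/15 = 6.7 percentage points, and could turn 2/15 into the rejecting 3/15. That is true of any single misclassification and says nothing about how often this one occurs. A response reached before transformation is legitimate.

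A reader might also apply the 20-30% transformation figure of Section 2.1 to all 29 patients (0.20 × 29 = 5.8; 0.30 × 29 = 8.7) and conclude that 6 to 9 are affected. That figure has no time frame, and it does not separate out patients who meet other criteria, start other therapy or die. It is not the affected number.

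Two cautions on any remedy also stand. The documents give 20% as a ceiling for CMML, not as a definition of AML. Blood counts alone can mislead, since Section 6.3.1 reports leukemoid reactions to cobimetinib and permits growth factors.

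**Conclusion.** The point holds for PFS. As written, the plan can score a patient with documented transformation as progression-free until further criteria, other treatment or death, and this conflicts with the weight that Section 2.1 gives to AML. This follows from the text of Appendix 3 and needs no assumption beyond reading progression in the PFS definition as Appendix 3 progression.

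The size can be given only in part. No blast rise alone is progression, and for baselines of 14% to 19% there is a further band, reaching as far as 28.5%, in which no blast criterion is met. The share of patients with such baselines, the number who transform without meeting other criteria and the resulting delay are not in the documents. The route into ORR is possible but uncommon, and its size cannot be derived. It does not justify redefining the primary endpoint at this stage of an open-label trial in which study drug is already being stopped.

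**What to change.** - **PFS definition (Sections 1.2.3 and 11.6.2).** State that documented transformation to AML is a stand-alone PFS event, dated at first documentation. Documentation means blasts of 20% or more (the Table 1 ceiling) in marrow, or in blood with confirmation on repeat if seen only there, or an AML diagnosis reported at a follow-up contact.
- **PFS sensitivity analysis.** Report PFS by the published IWG rule unchanged.
- **ORR.** Leave the definition as it is. Add a sensitivity analysis that excludes any clinical benefit first credited on or after the date of transformation.
- **Discontinuation wording.** The sponsor should reconcile the progression wording in Section 6.4.1 with the PFS definition. No treatment rule is proposed here.

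**Cost.** A short addition to two sections and two sensitivity analyses. Marrow blasts are already recorded (Section 10.8.1). Blood blasts are needed for the CR criteria but are not listed in Table 6, so capture in the eCRF should be checked, and the follow-up contact needs a question on AML diagnosis. The primary PFS analysis would depart from the published table and may look slightly less favourable. The change also comes late, which is a further reason to show both versions. It would not systematically detect transformation after EOT, because follow-up has no scheduled blood or marrow test.

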Appendix 5: Patient Dosing Diary

Subject Number: _____

Date: _____

Cobimetinib should be taken once daily (every 24 hours \pm 4 hours) for 21 consecutive days (Days 1 to 21-treatment period); followed by a 7-day break (Days 22 to 28-treatment break). If a dose is missed outside of the dosing window, the dose should not be made up. If a dose is vomited, treatment should be continued as prescribed the following day and the dose should not be made up.

Day	Date	Time	Number of tablets taken	Comments
1		:		
2		:		
3		:		
4		:		
5		:		
6		:		
7		:		
8		:		
9		:		
10		:		
11		:		
12		:		
13		:		
14		:		
15		:		
16		:		

Short Title: CONCERTO

Version Date: 09DEC2025

17		:		
18		:		
19		:		
20		:		
21		:		
22		---:---	0	
23		---:---	0	
24		---:---	0	
25		---:---	0	
26		---:---	0	
27		---:---	0	
28		---:---	0	
29		:		
30		:		
31		:		

Patient Signature

Date

Short Title: CONCERTO

Version Date: 09DEC2025

